Purpose of Study	To assess the impact of continuous glucose monitoring versus standard of care (e.g. a finger-prick protocol using a glucometer) on clinical outcomes, healthcare utilization, and cost in patients with type I or II diabetes treated within the Reimagine Primary Care clinics.
Design	Parallel Randomized Controlled Trial
Research Designation	The team intends to consent patients, collect data, analyze and publish; this will likely be a research designation.
Study Duration	13 Months (November 1, 2018 – December 31, 2019)
Number of Subjects	We aim to recruit 125 patients, expecting 20% attrition rate by the six-month follow-up, yielding about 100 patients for analysis (Section 7.2 Sample Size and Power).
Description of Subject Population	Patients with diabetes treated within the Intermountain Healthcare Reimagine Primary Care program between 1 November 2018 through 31 December 2019.
Eligibility Criteria	
Inclusion Criteria: Patients with type 1 or type 2 diabetes, having a HbA1c $\geq 6.5\%$, currently using glucometers or are prescribed a glucose meter at their index encounter, treated within Intermountain Healthcare's Reimagine Primary Care (RPC) program, and being seen by an RPC provider during the period of 1 November 2018 to 31 December 2019. Patients must have access to a smart phone to download applications, have Bluetooth capabilities for data sharing, log/view their continuous glucose monitor (CGM) data, and to take an exit survey.
 
Exclusion Criteria: Patients who are pregnant, not classified as having diabetes based on A1c levels, presence of vascular disease, age >80 years, diagnosis of dementia, and patients not currently using a glucose meter to monitor their sugar levels (and not being provided during the consulting visit).

Screening and/or Recruitment Location	Patients will be recruited while in the waiting room at the Reimagine Primary Care Clinics by a CITI/HIPAA trained coordinator or contacted by phone as per phone script instructs. These persons will maintain recruitment logs and load data in Tableau for real-time evaluation.

Brief Description of Study Procedures	
This is a parallel randomized controlled trial. Eligible patients who consent will be randomized to one of two groups: (1) the intervention group who will be given a Dexcom G6 for CGM, or (2) the control group who will follow their current standard finger-prick protocol via a provided Contour Next ONE glucometer. The CGM group must download the Dexcom G6 and Clarity mobile apps for data capture, whereas the standard of care group will use the Contour Next mobile app for their respective readings.
 
The Dexcom G6 captures real-time, dynamic glucose data every five minutes. Devices used in this study are FDA approved and commercially available.

Primary Endpoint	Hemoglobin A1c (HbA1c) level
Secondary Endpoints	Glycemic variability per mean amplitude of glycemic excursion (MAGE), coefficient of variation of HbA1c, range of HbA1c, frequency of hypoglycemic events, healthcare utilization per count of inpatient/outpatient visits, cost of care, current HEDIS performance on diabetes and behavioral health measures, coding specificity for diabetes, emergency department visit per 1000 rate, overall and for patients with diabetes, and hospitalization per 1000 rate related to
	diabetes, and self-reported behavioral changes (e.g. feeling more empowered to self-manage care, engaged with changing healthcare behaviors, and patient perceptions of the technology).
Analysis Population(s)	Patients with diabetes treated at all Reimagine Primary Care facilities (Avenues Internal Medicine, Cottonwood Family Medicine, Cottonwood Senior Clinic, and Holladay Internal Medicine) from 1 November 2018 to 31 December 2019 will be included in this study.
Benefits	Successful demonstration of CGM will allow patients to manage their condition, which may avoid the highs and lows of glucose monitoring and make patients feel better. This may reduce healthcare utilization and cost for the patients and the healthcare system as a whole. Furthermore, general knowledge on how to engage with patients in remote monitoring pilots will be better understood through this study.
Risks	This study includes recruiting patients and data will be collected. To minimize any breach in of private information the team will store data within the enterprise data warehouse/medical record, REDCap, and on secured mobile applications from Contour Next and Dexcom. While all devices used are FDA approved, there could be challenges for new users when using the new Dexcom G6

1.0 INTRODUCTION

1.1 Background and Rationale

Approximately 30 million Americans, or 9% of the population has diabetes, a condition in which a person does not make enough insulin, or the body cannot use its own to effectively manage blood glucose levels [1]. Improper diabetes management is associated with severe comorbidities which include: heart disease, stroke, kidney disease, ocular problems, dental disease, nerve damage, and vascularity issues. The epidemic continues to challenge systems like Intermountain Healthcare, an accountable care organization (ACO), since diabetes cost \$327 billion per year (representing \$1 in every \$7 dollars spent) on healthcare in the United States [2]. Furthermore, people with diagnosed diabetes incur average medical expenditures of \$16,752 per year, of which about \$9,601 is directly attributed to diabetes [2]. New treatment options are needed to manage population health, especially with 84 million adults having been diagnosed with prediabetes diabetes [3].

In an effort to reduce the physical, economic and social burden of diabetes, several healthcare systems have evaluated the use of telehealth to monitor glucose levels. In a metanalysis by Lee et al., the authors demonstrated that telehealth interventions produced a small, but significant improvement in hemoglobin A1c (HbA1c) levels compared with usual care (mean difference: -0.55, 95% CI: -0.73 to -0.36) [4]. The Ontario Health Technology Advisory Committee also showed that the blood glucose home telemonitoring technologies they used yielded a statistically significant reduction in HbA1c of ~0.50% in comparison to usual care when used adjunctively to a broader telemedicine initiative for adults with type 2 diabetes [5].

Intermountain Healthcare has piloted continuous glucose monitoring (CGM) and continues to expand its digital health services. However, to date, these services have not been used in Reimagine Primary Care Clinics (Cottonwood Senior, Cottonwood Family Medicine, Avenues Internal Medicine, Holladay Internal Medicine) to treat at-risk patients. These patients have, on average, four comorbidities and represent a challenging cohort to treat. Furthermore, data from the first eight months of operations in the Reimagine Primary Care Clinics have reported 1723 diagnoses of diabetes and 560 cases of pre-diabetes (**Figure 1**). Understanding if these patients will use remote CGM technology, learning how real-time knowledge influences their behavior, and assessing the impact on cost, care and utilization, is critical prior to expanding the number of Reimagine Primary Care sites within Intermountain Healthcare.

1.2 Previous Work

Intermountain Healthcare has participated in two previous CGM studies with Drs. [name] and [name] (IRB #: 1050741 and 1050410). Each are described in detail below:

[figure not shown]
- *IRB #1050741* – This recently completed quality improvement study successfully recruited n=20 patients with Type 2 Diabetes Mellitus (T2DM) to evaluate an integrated, CGM-based lifestyle modification program for glucose management in patients >65 years of age. The team is currently evaluating the data, but results will highlight the importance of education, self-discovery, and the way that we engage with our patients.
- *IRB #1050410* – Each year there are approximately 3000 gestational diabetes mellitus (GDM) pregnancies in the United States— contributing to an additional \$10,200 per affected pregnancy in cost. Most concerning is that women who have had GDM are 7x more likely to develop type 2 diabetes than women who did not have GDM during their pregnancy, and at least 40% of women with GDM will develop this disease. Therefore, the goal of our second CGM pilot was to: (1) accurately predict which women are at risk, (2) optimize recruitment and enrollment, (3) provide behavioral support to promote adherence to interventions, and (4) collect actionable data.

In this study, n=403 women were consented (n=189 at Intermountain Medical Center and n=214 at LDS Hospital). [name] and her staff discovered through qualitative feedback that women will wear a CGM device, are excited to see their data, and did not expect compensation for participation. Data is still being analyzed by Savvysherpa to assess patient outcomes.

2.0 STUDY OBJECTIVES/PURPOSE OF THE STUDY

The purpose of this study is to assess the effect of using CGM versus a standard of care (e.g. traditional fingerprick protocol) in an at-risk, diabetic patient population. The impact will be measured in terms of clinical outcomes (e.g., HbA1c level, glycemic variability), health care utilization (inpatient/outpatient visits), self-reported patient perceptions, and costs. We expect that CGM will empower patients to better manage their diabetes—ultimately, improving their health and reducing the burden of disease.

Figure 1

In this study, patients with type I and II diabetes will record their blood glucose levels since the output of the Dexcom G6 and the Contour Next ONE measure interstitial glucose. However, as noted in the *3.0 Study Design*, although the American Diabetes Association has provided a conversion table in which $\text{blood glucose} = 28.7 \times \text{A1C} - 46.7$ [6], the current standard of care is to have patients directly measure their blood glucose in the clinic rather than approximating. Thus, patients enrolled in this study will track their glucose with the general hypothesis being that those who more consistently monitor their blood glucose levels (and avoid the high peak to valley changes), will have a lower HbA1c at the end of the study. This will be tested by having HbA1c levels measured at two distinct time points: (1) at the time of enrollment, and (2) at the end of the pilot (six months). HbA1c levels may also be checked at the study midpoint (three months) if determined to be current standard of care by the provider and this data will also be considered. The aims below are written for HbA1c to confirm to the current standard of care.

Aim 1: Assess impact of CGM on glycosylated hemoglobin levels

Specific Aim 1a (primary analysis): Measure the effect of CGM vs. standard finger-prick protocol on HbA1c

- **Hypothesis for Aim 1a:** The patient-level six-month reduction in HbA1c will be greater among those randomized to CGM than that among those randomized to standard finger-prick protocol.
- **Process for Aim 1a:** We will compare the distributions of the patient-level, six-month change in HbA1c between randomized groups using the two-sided Wilcoxon rank-sum test.

Specific Aim 1b: Measure the longitudinal change in mean amplitude of glycemic excursion (MAGE) in CGM

- **Hypothesis for Aim 1b:** The patient-level daily MAGE will decrease over six months of CGM.
- **Process for Aim 1b:** MAGE is a metric of glycemic variability that can be measured from CGM, but not from infrequent (daily) monitoring. Thus, among CGM patients only, we will measure the six-month longitudinal change in 24-hr average MAGE. Upon computing each CGM patient's daily MAGE, we will use patient-level hierarchical modeling (generalized linear mixed models) to estimate the overall sixmonth longitudinal trend in MAGE.

Specific Aim 1c: Measure longitudinal change in daily coefficient of variation (C_v) of blood glucose in CGM

- **Hypothesis for Aim 1c:** The patient-level daily C_v of blood glucose will decrease over six months of CGM.
- **Process for Aim 1c:** Like that of MAGE, C_v of blood glucose is a metric of glycemic variability that requires near continuous monitoring. Thus, among CGM patients only, we will measure the six-month longitudinal change in daily C_v of blood glucose using the standard equation: $C_v = \sigma/\mu$. Once we have computed each CGM patient's daily C_v of blood glucose, we will use patient-level hierarchical modeling (generalized linear mixed models) to estimate the overall six-month longitudinal trend in C_v of blood glucose. Additionally, we will report the patient- and group-level distributions in daily blood glucose extrema (i.e., minimum and maximum).

Specific Aim 1d: Measure longitudinal change in overall blood glucose range and “time in range” ($\max \text{Range} - \min \text{Range}$) in CGM

- **Hypothesis for Aim 1d:** The patient-level daily blood glucose range will decrease and time in range (which is defined by glucose levels from 70 to 180) will increase over six months of CGM usage.
- **Process for Aim 1d:** Again, like MAGE and C_v , the blood glucose range is a metric of glycemic variability that is most meaningful with near continuous monitoring. So, among CGM patients only, we will measure the blood glucose range for the i th day as $\text{Range}_i = \max \text{HbA1c}_i - \min \text{HbA1c}_i$, and then use patient-level hierarchical modeling (e.g., generalized linear mixed models) to estimate the overall six-month longitudinal trend in HbA1c range.

Specific Aim 1e: Measure the effect of CGM vs. the standard finger-prick protocol on frequency of hypoglycemic events

- **Hypothesis for Aim 1e:** The patient-level six-month reduction in frequency of hypoglycemic events will be greater among those randomized to CGM than that among those randomized to control.
- **Process for Aim 1e:** Measure the patient-level change in rate of hypoglycemic events as the patient-level slope of the six-month linear change in the so-called “intensity” (λ) of the estimated nonhomogeneous Poisson point process. Once we’ve computed each patient’s six-month linear change in λ , we will compare the distributions between randomized groups. Note that the motivation for measuring change in frequency as the slope of λ estimated from a non-homogeneous Poisson process is that it allows us to compare changes in frequency of hypoglycemic events between groups with different modes of monitoring (continuous vs daily).

Aim 2: Assess impact of CGM on healthcare utilization and cost

Specific Aim 2a: Measure the effect of CGM vs. standard finger-prick protocol on healthcare utilization

- **Hypothesis for Aim 2a:** The count of primary care, specialist, and emergency department visits or hospital stays over six months will be fewer among those randomized to CGM than that among those randomized to standard finger-prick protocol.
- **Process for Aim 2a:** For each patient, count their visits to a primary care provider or specialist or emergency department/hospital admission. Next, compare the distributions of visit counts between randomized groups using a Poisson test, aggregated as well as stratified by visit type. Other metrics for evaluating utilization may include: current HEDIS performance on diabetes and behavioral health measures, coding specificity for diabetes, emergency department visit per 1000 rate, overall and for patients with diabetes, and hospitalization per 1000 rate related to diabetes.

Specific Aim 2b: Measure the effect of CGM vs standard finger-prick protocol on cost

- **Hypothesis for Aim 2b:** The total variable cost associated with healthcare services/visits over six months will be fewer among those randomized to CGM than that among those randomized to standard fingerprick protocol.
- **Process for Aim 2b:** For each patient, measure total variable cost of associated healthcare services and visits. Then compare the distribution of costs between randomized groups using the Wilcoxon rank-sum test, a non-parametric analogue of Student’s *t*-test.

Aim 3: Qualitatively understand patient perspective of CGM

Specific Aim 3a: Record patients’ self-reported willingness to participate in a CGM pilot

- **Hypothesis for Aim 3a:** Greater than 80% of patients who will have been approached to participate in this study will consent to participation.
- **Process for Aim 3a:** The team will record the number of patients approached, consented and those that participate in this study. Metrics will be helpful for estimating future recruitment in other Reimagine Primary Care studies.

Specific Aim 3b: Understand patient satisfaction with CGM

- **Hypothesis for Aim 3b:** Patient’s will be satisfied with CGM device.
- **Process for Aim 3b:** Develop and deploy exit surveys targeting patients randomized to CGM to assess satisfaction with the CGM device and related digital health monitoring services.

Specific Aim 3c: Understand how CGM changed patient behavior

Hypothesis for Aim 3c: Patients will have felt empowered by CGM.

- **Process for Aim 3c:** Within the survey developed/deployed per Aim 3b, include 5-point Likert-based questions soliciting patient opinions and perspectives. Summarize those perspectives so that research investigators and operational leaders can use this information to change clinical operations (as needed).

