3.0 STUDY DESIGN

This is a pilot, parallel randomized controlled trial of CGM versus a standard finger-prick protocol among patients with type I and II diabetes treated at Intermountain Healthcare’s Reimagine Primary Care Clinics. Patients will

be eligible if their most recent HbA1c level is $\geq 6.5\%$ and they are either currently using a glucose meter or are prescribed a glucose meter at their index encounter. Upon consent, which will occur within in a private office/room within the Reimagine Care Clinic, patients will be randomized into one of two groups:

- **Intervention group:** CGM using a Dexcom G6 to measure glycosylated hemoglobin levels every five minutes. Patients will be asked to download the Dexcom G6 and Clarity applications (to have access to their real-time data) and be given a link to complete an exit survey in REDCap near the end of their study participation. Data will be sent via Bluetooth and then exported by the Intermountain research team into a Tableau (or similar) dashboard for data analysis/comparison (**Appendix A**)
- **Control group:** A standard finger-prick protocol that will require patients to continue with their daily fingerprick regimen established by their physician. This group will be given a Contour Next One meter to ensure that each patient is receiving the same level of accuracy by the same device. A review by Ekhlaspour et al of 17 glucose meters demonstrated wide variability, with only two devices achieving the 2013 ISO standard (with the most accurate being the Contour Next) [7]. Patients in the control group will be asked to download the Contour Next application which will send data via Bluetooth similar to above. Data will be aggregated, and protected health information removed prior to analysis (by Intermountain Healthcare and Savvysherpa). At the end of the study, patients will be asked to complete a short survey in REDCap about their willingness to participate in future studies (**Appendix A**).

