Randomization will be assigned *a priori* using a random number generator from Microsoft Excel. Sub-Investigator will then transcribe these numbers and order them individually in concealed envelopes and present them to the Research Coordinators to ensure the CRC is blinded. At time of consent the Research Coordinator will hand the patient the earliest numbered envelope to randomize. . Patients in both randomized groups will be given the devices and one month supplies to ensure compliance with the protocol. The Study Coordinator and patient will exchange contact information so that the CRC may resupply the patient with necessary equipment at the end of their month supply. The CRC may meet the patient at their Reimagine Care Clinic or off site for patient convenience. All patients are expected to participate for six months, which is near the minimum duration sufficient to measure clinically meaningful changes in hemoglobin A1c related to gradual behavioral changes (e.g., diet, exercise, insulin administration). Further, each patient will complete 2 mandatory blood draws and one elective blood draw at their designated Reimagine Care Clinic to evaluate HbA1c level changes over the course of the study. Baseline HbA1c must be completed on day of enrollment (± 2 days) which Intermountain Healthcare may choose to cover if not paid for by patient's SOC. An elective blood draw will be considered for data if completed at 3 months (± 1 week) and a third required blood draw upon study completion (± 2 weeks) which the study may also choose to cover if not SOC. 2 weeks from 180 enrollment) which the study may pay for if not covered by patient's SOC. We postulate that those that have a more consistent interstitial glucose profile (which avoid the high peak to valley swings), will have a more pronounced difference in pre and post HbA1c levels. Specific Aim #1 above will help our team understand the relationship between interstitial glucose and HbA1c, along with other outcomes of interest which include weight loss, alterations in diet, change in physical activity, etc.

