7.0 STATISTICAL ANALYSIS

This study is a parallel randomized control trial that will evaluate the impact of CGM versus a standard fingerprick protocol, between and within randomized groups. The primary analysis (Specific Aim 1a) will measure the intervention effect on six-month change in HbA1c. The quantitative secondary analyses will measure the withinpatient longitudinal change in glycemic variability among CGM patients (Aims 1b-d) as well as the intervention effect on hypoglycemic events, healthcare utilization and cost (Aims 1e, 2a-b) between randomized groups. Additionally, for each of these aims, we will conduct exploratory sensitivity analyses: measuring provider variability and its effect, as well as looking at patient-level heterogeneity of treatment effect (HTE) to describe

subgroups of patients in whom the benefit of CGM might be amplified or attenuated. Technical details are provided in Section 7.1 *Statistical Considerations*.

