7.1 Statistical Considerations

The primary analysis (Aim 1a) will measure the intervention effect on the patient-level six-month absolute reduction in mean HbA1c. Since not all patients will have their final HbA1c test at six months exactly, we will estimate each patient's six-month reduction in HbA1c by interpolating/extrapolating from their assessments, given that their HbA1c levels were assessed on at least two occasions: baseline, and >3 months post baseline. Then, among patients with a sufficient number of occasions of HbA1c assessments, we will estimate their sixmonth HbA1c using generalized linear mixed models with patient-level random slopes and intercepts, with appropriate link function and distributional family [8]. The quantitative secondary analyses (Aims 1b-e, 2a-b) will use outcomes related to the longitudinal change in various metrics of glycemic variability (MAGE, C_v , range) as well as the frequency of hypoglycemic events, healthcare utilization, and cost. The secondary analyses will also use longitudinal data analysis to assess whether there is a significant reduction in glycemic variability over six months (Aims 1b-d) among those randomized to CGM, whether there is a significant reduction in hypoglycemic events over six months (Aim 1e) among those randomized to CGM, and to assess whether overall healthcare utilization and costs differ between randomized groups [9]. Accordingly, specific aims 1b-e will rely heavily on longitudinal data analysis within a multilevel/hierarchical framework [10], specifically using generalized linear mixed models. In the sensitivity analyses, provider variability will be accounted for using three-level (provider, patient, occasion), quasi-Bayesian generalized linear mixed models [11]. Finally, the sensitivity analyses exploring HTE will use generalized additive models (GAM) to identify subgroups of patients for whom CGM is likely to have a differential effect [12-13].

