7.2 Sample Size and Power

Based on 2018 data pulled from Intermountain's diabetes registry, we estimate that the four RPC clinics (Cottonwood FM, Cottonwood Sr, Holladay IM, and Avenues IM) will see about 30, 22, 17, and 6 study-eligible, unique patient encounters per month, respectively, yielding up to about 75 recruitable patients per month (up to 225 over three months of enrollment). We estimate that enrolling 125 patients – expecting 20% attrition by the sixth-month follow-up, yielding 100 patients for analysis – would be sufficient to achieve >80% power for the primary analysis (absolute reduction in HbA1c) if the standardized difference d of the effect size is >0.8 (**Figure 2**). Here, the standardized difference d is measured in terms of the difference between the randomized group-level means of six-month changes in HbA1c. So, for example, a standardized difference d in the effect size of 0.8 might be observed if the true effect size is, say, -1 (that is, if the difference between the means is -1) and the standard deviation of change is 1.25. Details of the power analysis will be made available upon request.

[figure not shown]

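### The primary HbA1c test is valid but ignores the mandatory baseline value except by subtraction; a baseline-adjusted rank test with a mean difference and 95% CI would be a cheap improvement

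*Combined protocol and SAP*

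**What the plan says.** - **Test.** Section 2.0, Aim 1a: "We will compare the distributions of the patient-level, six-month change in HbA1c between randomized groups using the two-sided Wilcoxon rank-sum test". No covariate or stratum is named.
- **Baseline.** Section 3.0: "Baseline HbA1c must be completed on day of enrollment", with a two-day allowance either way. The covariate is therefore planned for every patient. Under the same section patients will "be eligible if their most recent HbA1c level is" at least 6.5%.
- **Six-month value.** Section 7.1 obtains each patient's "six-month reduction in HbA1c by interpolating/extrapolating from their assessments", and then estimates the six-month value "using generalized linear mixed models with patient-level random slopes and intercepts". It names neither a treatment term nor a baseline covariate, so this model constructs the outcome and does not adjust the group comparison.
- **Effect.** Section 7.0: "The primary analysis (Specific Aim 1a) will measure the intervention effect on six-month change in HbA1c". Section 7.2 says the standardized difference d is "measured in terms of the difference between the randomized group-level means of six-month changes in HbA1c". No section names an estimator or a confidence interval for the primary endpoint.
- **Other models.** Sections 7.0 and 7.1 add three-level provider models and generalized additive models for each aim. These are exploratory sensitivity analyses and name no baseline HbA1c covariate.

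**The concern.** Subtracting baseline uses it, but with the slope fixed at 1. If the true slope of final on baseline HbA1c is anything else, change still depends on baseline and the rank test carries variation that could be removed. With about 100 analysed patients, a value that is already collected could add precision without further recruitment.

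The second gap is in reporting. The plan promises to measure an effect and sizes the study on a mean difference, yet the only comparison method named is a rank test. Its p-value does not tell a reader how many HbA1c points the device is worth, or how uncertain that figure is. This gap holds whatever the slope or correlation.

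**Working it through.** **Inputs.** From 7.2: 125 enrolled, 20% attrition, illustrative mean difference 1, SD of change 1.25. From 1.1: an effect of 0.55 ("mean difference: -0.55, 95% CI: -0.73 to -0.36", a telehealth meta-analysis), used here only as an illustration. Assumed because the documents do not state them: two-sided 0.05, 1:1 allocation, and the baseline-to-final correlation ρ. Unless noted, the calculations take two observed, normally distributed HbA1c values.

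**1. The plan's own figure.** 125 × 0.80 = 100, so 50 per arm; d = 1/1.25 = 0.8. The standard error of the mean difference is 1.25 × √(2/50) = 0.25. Power by the normal formula is Φ(1/0.25 − 1.96) = Φ(2.04) = 97.9%. With the Wilcoxon efficiency of 0.955 it is Φ(4 × √0.955 − 1.96) = Φ(1.95) = 97.4%. The plan's claim of more than 80% holds comfortably. 100 patients give 80% power at d of about 0.56 to 0.57, which is 0.70 to 0.71 points (× 1.25).

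**2. What adjustment removes.** With equal SD σ at both visits, the variance of change is 2σ²(1 − ρ) and the residual variance of final on baseline is σ²(1 − ρ²). Their ratio is (1 + ρ)/2. At 0.55 points, planned power is Φ(0.55/0.25 × √0.955 − 1.96) = Φ(2.15 − 1.96) = 57.5%. Adjusted power is Φ(2.15/√ratio − 1.96). The simulated columns use 10,000 trials per cell.

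| ρ | Variance ratio | Adjusted, formula | Planned, simulated | Adjusted rank test, simulated |
|---|---|---|---|---|
| 0.4 | 0.70 | 73% | about 56% | about 71% |
| 0.6 | 0.80 | 67% | about 56% | about 65% |
| 0.8 | 0.90 | 62% | about 56% | about 60% |
| 0.9 | 0.95 | 60% | about 56% | about 58% |

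Null rejection of the adjusted test stayed at 0.045 to 0.054. A different adjusted rank test (Quade), at a 0.5-point effect, showed the same pattern: about 49% planned against 65%, 60%, 54% and 51% at ρ 0.3, 0.5, 0.7 and 0.9.

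**3. How far this carries.** Holding the SD of change at 1.25 with equal SDs implies a baseline SD of 1.25/√(2(1 − ρ)) = 1.14, 1.40, 1.98 and 2.80 at the four correlations. If instead the population SD is set at 1.3 to 1.5 at both visits and the 6.5% entry cut is applied to baseline, the SD of change is no longer 1.25. Planned against adjusted power at 0.55 points is then:

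| ρ | SD of change after cut | Mean 7, SD 1.5 | Mean 8, SD 1.3 |
|---|---|---|---|
| 0.4 | 1.35–1.50 | 43 v 50% | 49 v 59% |
| 0.6 | 1.12–1.26 | 56 v 60% | 66 v 72% |
| 0.8 | 0.81–0.92 | 82 v 83% | 90 v 92% |
| 0.9 | 0.58–0.66 | 97.7 v 97.8% | 99.7 v 99.8% |

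These cells carry simulation error: a repeat of the first gave 43 v 48%. The gain is roughly 4 to 10 points at ρ 0.4 to 0.6, and at most about 2 at ρ 0.8 to 0.9, where the planned test already exceeds 80%.

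**4. Less favourable cases.** With baseline SD 0.8 times final SD and SD of change 1.25, power moves from 56.3, 57.1, 56.3 and 57.2% to 63.3, 59.0, 56.0 and 58.7%. Those are gains of 7.0, 1.9, −0.3 and 1.5 points. With a slope of exactly 1, adjustment loses 0.3 to 1.1 points. At d = 0.8 with equal SDs, power goes from about 97% to between 97.7 and 99.7%.

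**5. Why keep a rank test.** With equal SDs and a 0.55-point effect, a linear model used alone as the test can lose clearly to the planned Wilcoxon: 68% v 79% with t3 residuals at ρ 0.8, and 61% v 71% with gamma residuals at ρ 0.9.

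**6. Precision of the estimate.** The 95% CI half-width for the unadjusted mean difference is 1.96 × 0.25 = 0.49. Multiplying by √ratio gives 0.41, 0.44, 0.46 and 0.48 at the four correlations.

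**The case against.** The strongest reply is that nothing is broken. The test is valid, the Aim 1a hypothesis is itself written on change, and 3.0 calls the study a pilot. At the effect 7.2 sizes for, power is about 97%, so adjustment has little left to add. The larger gains appear only at an effect quoted in 1.1 for telehealth, which the plan does not adopt, and at correlations the documents do not give. The figures also concern two observed values, whereas 7.1 uses interpolated or model-estimated ones. All of this stands. It limits the point to an efficiency and reporting improvement.

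A second reply is that a rank test and a linear-model CI can disagree. With equal SDs and a 0.55-point effect, the adjusted rank test rejected while the CI included zero in 15 to 19% of trials with t3 residuals and 13 to 15% with gamma residuals, against about 2% under normality. This also stands, and the fix needs a rule for it. A Hodges–Lehmann shift with CI would match the planned test more closely, but 7.2 is written on the mean-difference scale.

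A reader might infer that the planned test is invalid, or that omitting the covariate leaves the trial short of its power target. The documents support neither: the rank-sum test on change keeps its type I error, and the power claim in 7.2 reproduces. A reader might equally take the mixed model in 7.1 as already adjusting for baseline. The text gives it no such role.

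**Conclusion.** The point holds as a cheap improvement, not as an error. The primary comparison leaves a mandatory baseline value unused beyond subtraction, and it lacks an effect estimate with CI on the scale the plan itself uses.

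The power gain at the illustrative 0.55-point effect runs from about 15 points (ρ 0.4, equal SDs, SD of change fixed at 1.25) down to nil. It is at most 2 to 3 points at d = 0.8, and becomes a loss of up to about 1 point if the slope is 1. These sizes rest on assumed ρ, visit SDs, alpha and allocation. They are not demonstrated for the 7.1 estimated value. The case for reporting a mean difference with CI depends on none of these assumptions.

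**What to change.** In Aim 1a and 7.1, before outcomes are seen:

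1. **Primary test:** regress observed end-of-study HbA1c on baseline HbA1c with the arms pooled and no arm term, then apply the two-sided Wilcoxon rank-sum test to the residuals.
2. **Effect size:** report beside it the baseline-adjusted mean difference with 95% CI from a linear model of the same observed value on arm and baseline.
3. **Decision rule:** state that the rank test decides significance, and that the mean difference is descriptive if the two disagree.
4. **Sensitivity analyses:** keep the unadjusted Wilcoxon test on change, and the analysis using the 7.1 estimated value. State how patients without an observed end-of-study value are handled.

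**Cost:** no new patients, visits or data. It needs revised wording, slightly more analysis work, and acceptance of up to about 1 point of power lost if the slope is near 1.
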